### 11.1 Sample Size and Randomization

Our power calculations give the minimally detectable intervention effects for endpoints in Primary Specific Aims, setting two-sided alpha error at 5% and power at 80%. We have set a sample size of 100 in each of the intervention and control arms, based both on our overall evaluation of minimum detectable differences across the range of study endpoints and on a reasonable estimate of the number of men we can recruit. The sample size allows for a drop-out rate of 5%, and power calculations assume correlations of 0.70 between baseline and follow-up measures.

Table 4 gives the minimally detectable differences between treatment arms for serum and tissue biomarkers of glucose regulation. We have used a variety of data sources to complete these tables, attempting whenever possible to use data generated from human studies. For serum biomarkers of glucose regulation, we use data from our own pilot study and the PCPT, and for tissue expression of IR/IGF-R1 and AKT we use data from Cox et al. The minimum detectable intervention effects range from 5.3% for serum glucose to 33.1% for insulin. Previous studies have shown that dietary change can induce the following intervention effects: 7% for fasting glucose, 40% for insulin and 2.2 % for adiponectin. Our pilot study based on the DPP demonstrated an intervention effect of ↑9.7% for IGFBP3, ↓38% for insulin and ↓14% for C-peptide. Based on these observations, we will have good power to detect changes in all serum biomarkers of glucose regulation, consistent with those seen in other human intervention studies.

For expression of IR, IGF-1R and AKT on surveillance prostate biopsies, the minimum detectable intervention effects are 29.2%, 46.3% and 26.5%, respectively. Previous experimental studies in animals have

**Table 4. Minimal detectable differences in serum and tissue biomarkers at 80% power,  $\alpha=0.05$  given a sample size of 200 (100 in each of the lifestyle intervention and control arms)**

Biomarker	Baseline Mean (SD) or n (%)	Minimum Detectable Difference (MDD)	
		Mean	% of mean
Primary Aim 1 - Serum			
Fasting glucose, mg/dL	106.3 (12.6)	5.6	5.3%
Primary Aim 2 - Serum			
C-peptide, ng/mL	1.7 (1.2)	0.54	31.6%
Insulin, pmol/L	138.0 (102.0)	45.7	33.1%
IGF-1, ng/mL	232.7 (75.4)	33.8	14.5%
IGF-BP3, ng/mL	4317.6 (975.2)	436.5	10.1%
Adiponectin, ug/mL	6.1(3.9)	1.8	29.0%
Primary Aim 3 – Tissue			
Insulin receptor	30 (34)	13.9	29.2%
IGF-1 receptor	112 (80)	32.7	46.3%
AKT	128 (83)	33.9	26.5%

shown the following results: a low-fat/low-carbohydrate diet can reduce expression of IR; low-fat, or caloric restriction diets can reduce expression of IGF-1R by 40%; and low-fat and/or low-carbohydrate and no carbohydrate diets reduce expression of AKT by up to 60%. Based on these observations, we have very good power to detect changes in IR, IGF-1R and AKT expression on epithelial cells from PCa biopsies.

Table 5 indicates the minimal detectable differences in change, and the power to detect a 5-point change between arms for each QOL tool. For most HRQOL assessments, we have good power to detect the designated minimally important differences (5-points) in QOL scores. Analyses of the association between the intervention and adverse pathology are exploratory in nature; thus, power is limited for this endpoint. Based on our clinical experience, approximately 25% of patients have 'adverse pathology' on their follow-up biopsy. Given the sample size in this study, we will be able to detect a 15% difference between intervention and control arms in the proportion of participants with adverse pathology on follow-up biopsy.

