**Table 5. Power and MDD for QOL**

QOL tool	Baseline Mean (SD)	Mean MDD	Power to detect
			5-point difference in score
MAX-PC	14 (9) 	4.0	97%
EQ-5D	86 (15) 	6.7	63%
EPIC-Urinary bother	86 (14) 	6.3	69%
EPIC-Sexual bother	63 (23) 	10.3	32%

All study documents (e.g., patient files, signed informed consent forms, copies of CRFs, Essential Document and Study Reference Binders) must be kept secured.

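### The MDDs in Tables 4 and 5 do not follow from the stated correlation of 0.70 and sample size; Table 5's MDD and power columns disagree, and the HRQOL power claim conflicts with the table

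*Combined protocol and SAP*

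**What the plan says.** Section 11.1 describes the calculations as "setting two-sided alpha error at 5% and power at 80" per cent, with 100 men per arm and a 5% drop-out allowance. It adds that "power calculations assume correlations of 0.70 between baseline and follow-up measures", and the synopsis (Rationale for Number of Subjects) repeats this. No other correlation and no other per-arm number appears.

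Section 11 (Primary Aims 1 to 3, Secondary Aim 1) makes the comparison a two-sided t-test on change from baseline, with a Wilcoxon test as the fallback for the biomarkers.

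Table 4's caption says its MDDs are at 80% power "given a sample size of 200 (100 in each of the lifestyle intervention and control arms"). The text summarises the serum rows as "The minimum detectable intervention effects range from 5.3% for serum glucose to 33.1% for insulin" and says of the tissue rows (insulin receptor, IGF-1R, AKT) that "the minimum detectable intervention effects are 29.2%, 46.3% and 26.5%, respectively".

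Table 5 ("Power and MDD for QOL") gives, for each tool, a mean MDD and the power for a 5-point difference. The text concludes: "For most HRQOL assessments, we have good power to detect the designated minimally important differences (5-points) in QOL scores". Secondary Aim 1 sets 5 points as the minimally important difference.

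**The concern.** Section 11.1 rests the choice of 100 per arm partly on the MDDs across endpoints. A reader should therefore be able to rebuild them from the stated inputs, and cannot. The printed MDDs are too large for a correlation of 0.70, and the serum and tissue rows imply different correlations. The two columns of Table 5 do not describe the same calculation, and the HRQOL sentence does not describe Table 5.

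Some conclusions depend on which input is right. "Our pilot study based on the DPP demonstrated an intervention effect of" a 9.7% rise in IGF-BP3, which is below the printed MDD of 10.1% but above the 7.1% that 0.70 would give. Whether most HRQOL tools have adequate power also turns on the correlation.

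**Working it through.** **Inputs.** Two-sided alpha 5%, power 80%, r = 0.70, 100 per arm less 5% = 95 evaluable (section 11.1); t-test on change (section 11); baseline SDs and printed MDDs (Tables 4 and 5). Assumption: the follow-up SD equals the baseline SD, since the tables give only baseline SDs.

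**Formula.** The SD of change is SD × √(2(1 − r)). The MDD for a two-sample t-test on a variable with SD 1 (non-central t) is 0.4086 at 95 per arm and 0.3981 at 100. Hence:

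- r = 0.70, 95 per arm: 0.4086 × √0.6 = 0.316 SD
- r = 0.70, 100 per arm: 0.3981 × √0.6 = 0.308 SD
- r = 0.50, 95 per arm (same as the raw SD with no correlation): 0.4086 × √1.0 = 0.409 SD
- r = 0.40, 95 per arm: 0.4086 × √1.2 = 0.448 SD

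**Trying to reproduce the printed MDDs (95 per arm).**

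| Row | SD | Printed MDD | Printed/SD | r = 0.70 | r = 0.50 | r = 0.40 |
|---|---|---|---|---|---|---|
| Glucose | 12.6 | 5.6 | 0.444 | 3.99 | 5.15 | 5.64 |
| C-peptide | 1.2 | 0.54 | 0.450 | 0.38 | 0.49 | 0.537 |
| Insulin | 102 | 45.7 | 0.448 | 32.3 | 41.7 | 45.65 |
| IGF-1 | 75.4 | 33.8 | 0.448 | 23.9 | 30.8 | 33.75 |
| IGF-BP3 | 975.2 | 436.5 | 0.448 | 308.6 | 398.5 | 436.49 |
| Adiponectin | 3.9 | 1.8 | 0.462 | 1.23 | 1.59 | 1.75 |
| Insulin receptor | 34 | 13.9 | 0.409 | 10.8 | 13.89 | 15.2 |
| IGF-1 receptor | 80 | 32.7 | 0.409 | 25.3 | 32.69 | 35.8 |
| AKT | 83 | 33.9 | 0.408 | 26.3 | 33.91 | 37.1 |
| MAX-PC | 9 | 4.0 | 0.444 | 2.85 | 3.68 | 4.03 |
| EQ-5D | 15 | 6.7 | 0.447 | 4.75 | 6.13 | 6.71 |
| Urinary bother | 14 | 6.3 | 0.450 | 4.43 | 5.72 | 6.27 |
| Sexual bother | 23 | 10.3 | 0.448 | 7.28 | 9.40 | 10.29 |

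No row fits r = 0.70. At 95 per arm the serum and QOL rows fit r = 0.40. Adiponectin is the loosest, but an unrounded SD of 3.95 would give 1.77 and the printed 29.0%. The tissue rows fit r = 0.50. These correlations are inferred, not documented. At 100 per arm the implied values are about 0.37 and 0.47. Also, 0.448 SD equals r = 0.70 with 48 per arm, but the tissue rows would then need about 57.

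**As a percentage of the mean, r = 0.70 against printed.** Glucose 3.8 (5.3), C-peptide 22.3 (31.6), insulin 23.4 (33.1), IGF-1 10.3 (14.5), IGF-BP3 7.1 (10.1), adiponectin 20.2 (29.0), AKT 20.5 (26.5). For the two receptors the printed percentages are transposed: 13.9/30 = 46.3% belongs to the insulin receptor and 32.7/112 = 29.2% to IGF-1R. The r = 0.70 values to compare with these are 35.9% and 22.6%. As printed, the IGF-1R MDD of 46.3% exceeds the 40% animal effect cited in support of very good power; the correct 29.2% does not.

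**Table 5, columns against each other.** An 80% MDD fixes the power at 5 points, whatever the SD or r: power = Φ(5 × 2.80/MDD − 1.96). For EQ-5D, 5 × 2.80/6.7 − 1.96 = 0.13, so power is 55%.

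| Tool | Printed MDD | Power it implies | Printed power | r = 0.70 | r = 0.50 | r = 0.40 |
|---|---|---|---|---|---|---|
| MAX-PC | 4.0 | 94% | 97% | >99% | 97% | 94% |
| EQ-5D | 6.7 | 55% | 63% | 84% | 63% | 55% |
| Urinary bother | 6.3 | 60% | 69% | 89% | 69% | 61% |
| Sexual bother | 10.3 | 27% | 32% | 49% | 32% | 27.5% |

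Rounding of the MDDs moves the implied powers by less than one point. The power column matches r = 0.50 and the MDD column r = 0.40; neither is 0.70.

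**HRQOL sentence.** Three of the four printed MDDs exceed 5 points, and only MAX-PC reaches 80%. At 95 per arm, 80% power for 5 points needs r of at least 0.667 (EQ-5D), 0.618 (urinary bother) and 0.858 (sexual bother). Three of four tools therefore qualify only if r is about 0.67 or more.

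**IGF-BP3.** Power for the pilot effect of 9.7% (418.8 ng/mL) is 97% at r = 0.70 and 77% at r = 0.40.

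**The case against.** *Another method might explain the tables.* Baseline-adjusted analysis does not: its factor is √(1 − r²), giving 0.4086 × √0.51 = 0.292 SD at r = 0.70, and at 95 per arm it cannot exceed 0.409 SD at any r. Unequal SDs do not either. With follow-up SD k times baseline, the variance of change is 1 + k² − 1.4k; reaching 0.448 SD needs (0.448/0.4086)² = 1.20, so k is about 1.5 in the serum and QOL rows. Forty-eight per arm would fit those rows, but it is about half the stated number.

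*Table 5 states no power level, and section 11.1 introduces 80% and 0.70 for the primary aims.* This is fair, and whether 0.70 was meant for Table 5 is unclear. Yet 80% is the only level the plan gives, and Table 5 shares the serum rows' ratio of about 0.448. The two columns agree only if the MDDs were for about 87% power: for EQ-5D, (1.96 + 0.33) × 6.7/5 − 1.96 = 1.11. That level is stated nowhere.

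*The consequence is small.* Largely true. If 0.70 holds, the printed MDDs are conservative, and glucose is safe either way because 3.8% and 5.3% are both below the cited 7%. The pilot insulin effect of 38% has about 90% power or more at either r, and C-peptide at 14% is short at both (42% and 24%). For IGF-BP3, 77% against 80% is a modest shortfall. Good power is not defined, and Table 5 already discloses 32% for sexual bother. Still, printed powers of 63%, 69% and 32% do not support the word most.

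**Conclusion.** The concern holds. At the stated r and 95 per arm, the printed MDDs are 40% to 46% too large for the serum and QOL rows and 29% too large for the tissue rows. Table 5's printed powers exceed those its own MDDs imply by about 3 to 9 percentage points. One of four HRQOL tools, not most, reaches 80% in the table as printed.

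This rests on a t-test on change, equal baseline and follow-up SDs, and Table 5's MDDs being at 80% power. The documents do not show which input is wrong. The finding does not show that the trial is too small: it shows that the stated inputs, the tables and the HRQOL sentence cannot all be right, and that the IGF-BP3 and HRQOL power statements depend on which one is.

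**What to change.** 1. State the correlation(s) actually assumed, by endpoint group if they differ, and say whether they cover Table 5. State the evaluable number per arm and the power level for Table 5's MDDs.
2. Recompute every MDD and power in both tables from those inputs. The tables above give the results for 0.70, 0.50 and 0.40 at 95 per arm; the last two are inferred and should not be adopted without a source.
3. Correct the transposed insulin receptor and IGF-1R percentages, in Table 4 and in the text of section 11.1.
4. Rewrite the HRQOL sentence to match the recomputed table, and say that sexual bother is underpowered for 5 points under any of these correlations (28% to 49%).

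The cost is two recomputed tables and about three sentences. No change in sample size is needed.

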## 5 CRITERIA FOR EVALUATION

### 5.1 Primary Endpoint

The primary endpoints for each of the primary aims are:

**Primary Aim 1:** change in fasting glucose levels relative to baseline between the intervention and control arms.

**Primary Aim 2:** change in fasting C-peptide, insulin, IGF-1, IGF-BP3, and adiponectin levels relative to baseline between the intervention and control arms.

**Primary Aim 3:** change in expression of IR, IGF-1R, and AKT on prostate cancer epithelial cells from follow-up surveillance biopsy (6 months post-randomization) relative to 'baseline' (biopsy ~6 months prior to randomization).

**Primary Aim 4:** will test whether PCa patients randomized to the intervention arm are able to sustain the beneficial changes in weight and glucose regulation an additional 6 months after the active intervention.

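### Section 11.1 claims good power for every serum marker, but its own figures show low power for C-peptide and adiponectin, both Primary Aim 2 endpoints

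*Combined protocol and SAP*

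**What the plan says.** Section 5.1 defines the Primary Aim 2 endpoint as "change in fasting C-peptide, insulin, IGF-1, IGF-BP3, and adiponectin levels relative to baseline between the intervention and control arms". Section 11.1 sets 100 men per arm, two-sided 5% alpha, 80% power and 5% drop-out, and states that "power calculations assume correlations of 0.70 between baseline and follow-up measures". Table 4 then lists a minimum detectable difference (MDD) for each marker.

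The text next to the table gives the effects regarded as plausible. From previous dietary studies it takes "7% for fasting glucose, 40% for insulin and 2.2 % for adiponectin". From the sponsor's own pilot it reports "an intervention effect of ↑9.7% for IGFBP3, ↓38% for insulin and ↓14% for C-peptide". On the strength of these it concludes that "we will have good power to detect changes in all serum biomarkers of glucose regulation". No other section qualifies that sentence or gives larger expected effects for C-peptide or adiponectin.

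**The concern.** A claim of adequate power at cited effects can be true only if each effect is at least about as large as the corresponding MDD. For C-peptide and adiponectin it is not: the cited effects are 0.44 and 0.08 of the Table 4 values. No effect at all is cited for IGF-1.

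What is at stake is how the Aim 2 results will be read. This sentence is the plan's only conclusion on power for the serum markers. A reader who trusts it would take a non-significant C-peptide or adiponectin result as evidence that the intervention does not move that marker. If the cited effects are real, such a result is the more likely outcome for both.

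**Working it through.** **Inputs.** Table 4 baseline means and SDs; the cited effects in section 11.1; 100 per arm less 5% = 95 evaluable per arm; two-sided 5%; a t-test on change from baseline (section 11, Primary Aim 1, carried over to Aim 2). Cited percentages are applied to the Table 4 baseline means, the scale on which Table 4 expresses its own MDDs.

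**Step 1: reproduce Table 4.** The SD of change is SD × √(2(1−r)). With 95 per arm, the non-central t gives an 80%-power MDD of 0.4086 SDs of change.

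- At r = 0.70 (stated): √0.6 = 0.7746, so MDD = 0.4086 × 0.7746 = 0.3165 baseline SD. C-peptide: 0.3165 × 1.2 = 0.380, and 0.380/1.7 = 22.3%. Table 4 has 31.6%.
- At r = 0.40: √1.2 = 1.0954, so MDD = 0.4476 baseline SD. C-peptide: 0.4476 × 1.2 = 0.537, or 31.6%, which matches. The other serum rows come out at 5.64, 45.7, 33.7, 436.5 and 1.75, against 5.6, 45.7, 33.8, 436.5 and 1.8 in the table.

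The serum rows therefore correspond to a correlation of about 0.40, not the stated 0.70. That is a separate inconsistency, so both values are carried through.

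**Step 2: compare using the plan's figures alone.** Power is approximately Φ(2.80 × effect/MDD − 1.96), plus the opposite tail.

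- C-peptide: 14/31.6 = 0.443; Φ(−0.72) ≈ 24%.
- Adiponectin: 2.2/29.0 = 0.076; Φ(−1.75) plus the opposite tail ≈ 5.5%.

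**Step 3: power by non-central t, 95 per arm, 188 df.** For C-peptide at 0.70, the effect is 0.14 × 1.7 = 0.238 and the SD of change is 1.2 × 0.7746 = 0.930. The non-centrality is (0.238/0.930) × √(95/2) = 1.76, and power is 42%. The same steps for the other markers give:

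| Marker | Cited effect | Table 4 MDD | MDD at r = 0.70 | Power, r = 0.70 | Power, r = 0.40 |
|---|---|---|---|---|---|
| Glucose, mg/dL | 7% = 7.4 | 5.6 (5.3%) | 3.99 (3.8%) | >99% | 96% |
| Insulin, pmol/L | 38% = 52.4 | 45.7 (33.1%) | 32.3 (23.4%) | >99% | 90% |
| IGF-BP3, ng/mL | 9.7% = 419 | 436.5 (10.1%) | 308.6 (7.1%) | 97% | 77% |
| C-peptide, ng/mL | 14% = 0.238 | 0.54 (31.6%) | 0.380 (22.3%) | 42% | 24% |
| Adiponectin, ug/mL | 2.2% = 0.134 | 1.8 (29.0%) | 1.23 (20.2%) | 6% | 6% |
| IGF-1, ng/mL | none | 33.8 (14.5%) | 23.9 (10.3%) | – | – |

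**Step 4: can another reading rescue the claim?**

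- ANCOVA at 0.70, with SD × √(1−r²): 48% for C-peptide, 6% for adiponectin.
- No allowance for drop-out (100 per arm, r = 0.70): 44% and 6%.
- C-peptide reaches 80% at a 14% effect only with a correlation of about 0.88, or with 241 evaluable men per arm at 0.70.
- Adiponectin at 0.70 needs about 7,955 per arm, or an effect about nine times larger (20.2/2.2 = 9.2).

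**The case against.** Five points can be made for the plan.

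- **Location.** The paragraph itself gives only an MDD range, 5.3% to 33.1%, and 14% lies inside it. The C-peptide contradiction appears only when Table 4 is read alongside. That is correct, but the paragraph introduces Table 4 and relies on it. For adiponectin the paragraph alone suffices, since 2.2% is below the smallest MDD in the range.
- **Precision for C-peptide.** Section 11 allows a Wilcoxon test if normality is doubtful, and an SD of 1.2 on a mean of 1.7 suggests skew. Simulations assuming a log-normal marker and a proportional 14% fall gave about 48% to 57% at 0.70 for the Wilcoxon test or a t-test on log change, and about 63% for log-scale ANCOVA. At 0.40 the first two gave about 30% to 32%. This stands: 42% is specific to the t-test on raw change. All these values remain below 80%.
- **The 2.2% may be wrong.** Its source is numbered beyond the end of the document's reference list, which stops at 85. The adiponectin result is therefore conditional on that figure. The C-peptide effect comes from the sponsor's own pilot and does not share this doubt.
- **Scale.** The plan does not say whether the cited percentages are between-arm or within-arm, or relative to which baseline. Applying them to Table 4's means is an assumption.
- **Weight.** The sample size was set partly by feasible recruitment, section 11 introduces the Aim 2 comparisons as additional analyses, and glucose (Aim 1) is well powered. All true, but the Aim 2 markers are still labelled primary, and feasibility does not make the power statement correct.

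**Conclusion.** The concern holds. On the plan's own numbers, the blanket claim is wrong for C-peptide and adiponectin. At the cited effects, the chance of a non-significant result is about 58% for C-peptide at a correlation of 0.70 (76% at 0.40) and about 94% for adiponectin at either value. The claim is sound for glucose and insulin. IGF-BP3 just misses on Table 4 but is adequate if 0.70 is right. For IGF-1 the claim is unsupported, not refuted.

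These sizes assume Table 4's means and SDs, 95 evaluable men per arm, a t-test on change, and cited percentages read as between-arm differences relative to baseline means. The direction does not depend on the choice of correlation or test among those examined. For adiponectin it does depend on 2.2% being the intended figure.

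**What to change.** Settle one baseline-to-follow-up correlation, confirm the 2.2% for adiponectin, and say what the cited percentages are relative to. Then replace the blanket sentence in section 11.1 with a short marker-by-marker list of cited effect, MDD and power under that correlation and a named test:

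- Limit the claim of good power to glucose, insulin and, if 0.70 is kept, IGF-BP3.
- State that power at the cited effects is low for C-peptide (42% at 0.70 with a t-test on raw change) and, if 2.2% is confirmed, for adiponectin (about 6%). Add that a non-significant result for either will be reported with its confidence interval and not read as evidence of no effect.
- State that no expected effect is cited for IGF-1.

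The protocol already does this elsewhere: section 11.1 concedes limited power for adverse pathology, and Table 5 gives power of 63%, 69% and 32% for individual quality-of-life scales.

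The cost is a wording amendment to one paragraph, plus recalculation of Table 4's serum rows if 0.70 is kept. No extra patients are needed, and endpoints, their hierarchy, tests and sample size stay as they are. The stated power becomes less favourable for two markers.

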## **11 STATISTICAL METHODS AND CONSIDERATIONS**

**Primary Aim 1.** The primary analysis will compare change in fasting glucose level relative to baseline between the intervention and control arms. Global assessment of intervention effects will be evaluated using a two-sided t-test or Wilcoxon rank sum test if normality of the measurement is questionable (as determined by QQ-normal plots). Further analysis will quantify effects of patient age, BMI and other body composition measures on change in fasting glucose using linear regression. Differential effects between intervention and control arms will be quantified using interaction terms. All analyses will compare effects based on intention-to-treat.

**Primary Aim 2.** Additional analyses will compare changes in levels of C-peptide, insulin, IGF-1, IGF-BP3, and adiponectin relative to baseline measurements between the intervention and control arms. As in Aim 1, we will compare global and subgroup effects based on intention-to-treat analyses.

**Primary Aim 3.** We will test whether the change in expression of IR, IGF-1R, and AKT on prostate cancer epithelial cells from follow-up surveillance biopsy (6 months post-randomization) relative to 'baseline' (biopsy ~6 months prior to randomization, see Fig. 3) differs between intervention and control arms. Global assessment of intervention effects will be evaluated using a two-sided t-test (or Wilcoxon rank sum test). Linear regression will be used to assess associations of IR, IGF-1R, and AKT expression with systemic measures of glycemic control at 6 months. Exploratory analyses will also evaluate associations between adverse pathology, biomarkers of glycemic control and IR/IGF-1R/AKT expression.

**Primary Aim 4.** We will test whether PCa patients randomized to the intervention arm are able to sustain the beneficial changes in weight and glucose regulation an additional 6 months after the active intervention. We will follow the DPP research group characterization of sustained weight loss as maintenance of a 7% reduction in weight and sustained glucose regulation as maintenance within 5% of 6-month levels. Because not all participants will achieve 7% weight loss at 6 months, we will look in the subset of participants who did and did not achieve this goal both separately and combined. A one-sample test of proportions will be used to determine whether the proportion of participants that are able to sustain lifestyle changes differs from zero.

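### The detectable percentages for insulin receptor and IGF-1 receptor in Section 11.1 do not match their own Table 4 rows (most likely transposed), and the strong power claim for insulin receptor is unsupported

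*Combined protocol and SAP*

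**What the plan says.** Primary Aim 3 (Section 3.1) asks whether the intervention lowers IR or IGF-1 receptor (IGF-1R) in tumour epithelium. Section 11.1 plans 100 men per arm, two-sided alpha of 5% and 80% power. It adds "The sample size allows for a drop-out rate of 5" per cent and that "power calculations assume correlations of 0.70 between baseline and follow-up measures". The Synopsis repeats both assumptions. Section 11 compares change from baseline between arms: "Global assessment of intervention effects will be evaluated using a two-sided t-test or Wilcoxon rank sum test" under Primary Aim 1, with the same choice of tests under Primary Aim 3.

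Table 4 gives these tissue rows, with the last column defined as the detectable difference (MDD) as a percentage of the baseline mean:

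| Marker | Mean (SD) | MDD | Printed % of mean |
|---|---|---|---|
| IR | 30 (34) | 13.9 | 29.2% |
| IGF-1R | 112 (80) | 32.7 | 46.3% |
| AKT | 128 (83) | 33.9 | 26.5% |

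The text gives the percentages in the same order: "the minimum detectable intervention effects are 29.2%, 46.3% and 26.5%, respectively".

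The benchmarks are from animal studies. For IR there is a direction without a size: "a low-fat/low-carbohydrate diet can reduce expression of IR". For IGF-1R, "caloric restriction diets can reduce expression of IGF-1R by 40" per cent. For AKT, "no carbohydrate diets reduce expression of AKT by up to 60" per cent. The section then concludes that "we have very good power to detect changes in IR, IGF-1R and AKT expression on epithelial cells from PCa biopsies".

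**The concern.** A percentage of the mean can be checked by dividing two numbers in the same row. In the IR and IGF-1R rows the division gives the other row's percentage. The text repeats the pair, so the error is not confined to one cell of the table.

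Aim 3 is a primary aim, and the sample size is justified partly by the detectable differences. A reader who later meets a null IR result would believe that a 29.2% change had been detectable with 80% power. The power sentence also conflicts with the figures beside it: as printed, the IGF-1R detectable effect of 46.3% exceeds the only IGF-1R effect cited, 40%.

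**Working it through.** **1. Row check (MDD divided by mean).**

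- IR: 13.9/30 = 46.3%; printed 29.2%. Rounding of the entries allows 13.85/30.5 = 45.4% to 13.95/29.5 = 47.3%.
- IGF-1R: 32.7/112 = 29.2%; printed 46.3%. Rounding allows 32.65/112.5 = 29.0% to 32.75/111.5 = 29.4%.
- AKT: 33.9/128 = 26.5%; matches.
- Serum rows (glucose, C-peptide, insulin, IGF-1, IGF-BP3, adiponectin): 5.3, 31.8, 33.1, 14.5, 10.1 and 29.5%; printed 5.3, 31.6, 33.1, 14.5, 10.1 and 29.0%. The C-peptide and adiponectin differences lie within rounding of their entries.

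Seven of nine rows agree. The other two hold each other's value to the decimal.

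**2. Do the absolute MDDs fit their SDs?** Inputs: 100 per arm less 5% drop-out = 95; two-sided 5%; 80% power; two-sample t-test. By noncentral t the MDD is 0.4086 × SD (the normal approximation gives (1.960 + 0.842) × √(2/95) = 0.407). On the unadjusted SD:

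- IR: 0.4086 × 34 = 13.89 (printed 13.9)
- IGF-1R: 0.4086 × 80 = 32.69 (printed 32.7)
- AKT: 0.4086 × 83 = 33.91 (printed 33.9)

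So MDD and SD cohere in each tissue row, and only the two percentages fail. That this basis was used is an inference. It equals a change score with correlation r = 0.50, since the SD of change is SD × √(2(1 − r)).

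**3. Can any usual basis give 29.2% for IR?** On the printed mean and SD with 95 per arm, a 29.2% change is 0.292 × 30 = 8.76 units.

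| Basis | IR MDD | % of mean | Power for 8.76 | Men per arm for 80% power |
|---|---|---|---|---|
| Unadjusted SD | 13.89 | 46.3% | 42% | 237 |
| Change score, r = 0.70 (SD × √0.6) | 10.76 | 35.9% | 63% | 142 |
| ANCOVA, r = 0.70 (SD × √0.51) | 9.92 | 33.1% | 70% | 121 |

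None does. With 80 evaluable pairs per arm (illustrative), power on the first two bases falls to 37% and 55%.

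**4. Power against the cited effects (95 per arm, unadjusted SD).**

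- IGF-1R, 40% of 112 = 44.8, SD 80: power 97%.
- AKT, 60% of 128 = 76.8, SD 83: power above 99.9%.
- IR: no effect size is given, so there is nothing to test. If the 40% cited for IGF-1R also applied to IR (an assumption), power would be 68%, or 88% for a change score at r = 0.70.

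**5. Basis of Table 4 as a whole.** A change score at the stated r = 0.70 with 95 per arm gives 0.4086 × √0.6 × SD:

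| Marker | At r = 0.70 | Printed |
|---|---|---|
| Glucose | 3.99 | 5.6 |
| C-peptide | 0.38 | 0.54 |
| Insulin | 32.3 | 45.7 |
| IGF-1 | 23.9 | 33.8 |
| IGF-BP3 | 308.6 | 436.5 |
| Adiponectin | 1.23 | 1.8 |
| IR | 10.8 | 13.9 |
| IGF-1R | 25.3 | 32.7 |
| AKT | 26.3 | 33.9 |

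No row matches. The printed MDDs are 0.41 SD for tissue and 0.44 to 0.46 SD for serum, so the table does not rest on one basis. A change score at r = 0.40 gives 5.64, 0.537, 45.65, 33.75, 436.5 and 1.75 for the six serum rows, which match the printed values within rounding of the SDs. That too is an inference.

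**The case against.** The direction of the error is not certain. The source data are not in the documents. If the mean, SD and MDD were entered under the wrong receptor, 29.2% would be right for IR and the problem would fall on IGF-1R. This stands, so every IR power figure here is conditional on the row entries being right. It does not rescue the power sentence: IGF-1R would then need 46.3% against a cited 40%, with power for 40% of about 68% (unadjusted SD) or 88% (change score, r = 0.70).

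The 46.3% and 42% figures use a basis that the protocol does not state. On the stated correlation the IR MDD is 35.9%, about 1.2 times the printed 29.2% instead of 1.6 times, and power is 63%. This is fair as to size, but 29.2% is still not reached. All the power figures are normal-theory approximations for a score that cannot be negative and has an SD above its mean, and the plan allows a rank test.

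The mismatch with r = 0.70 is a separate matter and is conservative: every printed MDD is larger than the stated basis would give. That is right. It is a fault of reporting, not a shortfall in sample size.

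The AKT benchmark also needs care. Table 2 in Section 1.3 lists reductions in phosphorylated Akt, while the Table 4 row is labelled AKT. The sponsor should confirm that the 60% refers to the same measure.

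Finally, the sample size rests on many endpoints and on feasible recruitment, and no stated IR target is missed. This limits the consequence, but a wrong planning figure for a primary aim still needs correcting.

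**Conclusion.** The point holds. The IR and IGF-1R percentages in Table 4 and the text contradict their own rows beyond rounding, and transposition is the most likely explanation. If the row entries are right, the IR MDD is 46.3%, 1.6 times the printed figure, and IGF-1R improves from 46.3% to 29.2%. Power for a 29.2% IR change is then 42% to 63% (unadjusted SD; change score at r = 0.70), assuming 95 evaluable paired biopsies per arm; fewer pairs would lower it.

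The joint power claim is supported for IGF-1R once corrected, and for AKT on the cited benchmark. For IR it is unsupported, though not disproved. Separately, Table 4 does not follow from the stated correlation, and its tissue and serum rows do not share a basis. The correction should be made, but neither the sample size nor the analysis is affected.

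**What to change.** 1. Check the IR and IGF-1R entries (mean, SD, MDD) against the source data.
2. If they are right, print IR 46.3% and IGF-1R 29.2% in both Table 4 and the text of Section 11.1.
3. Limit the strong power claim to IGF-1R and AKT, or say for IR that only changes at or above its MDD are detectable with 80% power.
4. For the whole of Table 4, state the variance and correlation basis actually used, or recompute all nine rows on one basis. If the rows are recomputed, the new percentages replace those in step 2 (for a change score at r = 0.70 and 95 per arm, IR 35.9%, IGF-1R 22.6%, AKT 20.5%). The tissue rows should not be recomputed alone.

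The cost is two percentages in two places, one sentence on power, and one statement of basis or nine recomputed MDDs. If the row entries are confirmed, the stated IR detectable effect becomes less favourable.
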